8.6 SAMPLE SIZE CALCULATION

A sample size of up to 300 eyes is planned to be enrolled, where a screen failure of up to 70 eyes (23%) is anticipated. Approximately 230 eyes will be randomized and implanted with toric or control IOL.

[REDACTED]

[REDACTED]

Given that all co-primary effectiveness endpoints must be met for study success, the worst-case study power, assuming independence among all tests, is $0.94 \times 0.99 \times 0.99 \times 0.99 = 91\%$. However, given any positive correlation among the endpoints, power will exceed 91%.

8.7 OTHER STATISTICAL METHODS

8.7.1 Pooling of Data for Analyses

The clinical study will be conducted under a common protocol for each investigational site with the intention of pooling the data for analysis. Every effort will be made to promote consistency in study execution at each investigational site. The analysis of homogeneity will be conducted under the assumption that each site will have enrolled a minimum of 3 All-implanted subjects in the test group and 3 All-implanted subjects in the control group. Sites with fewer than 3 subjects will be omitted from the poolability analysis.

The consistency of treatment response will be investigated across the analysis centers subsequent to combining the data as described above. Statistical tests will be conducted to identify if there are outlier analysis centers that could affect the interpretation of common statistical and clinical conclusions. One method is to see if the treatment effect (such as mean acuity difference between eye's UCDVA, BCDVA, and residual cylinder) is significantly different across analysis centers (ANOVA test at $\alpha = 0.15$, for visual acuity (VA) and Wilcoxon rank-sum test at $\alpha = 0.15$ for residual cylinder). If it's not significantly different, then results from the analysis centers will be pooled for further analysis; if the difference is statistically significant, an investigation will be

conducted to identify which analysis center has the extreme outcomes. In the event of one or more divergent analysis center(s) being identified, further clinical investigations will be conducted to find out probable causes for the extreme results that are external and unrelated to the study device, such as clinical staff inconsistency, inconsistent measurement technique, testing equipment malfunction and so on. If such a cause has been identified as the most plausible cause for the divergent treatment effects, the analysis center(s) with extreme results will be reported separately and will be excluded from the study-level results based on pooled data from the rest of the analysis centers.

It is noted that applying this process may exclude subjects from the analysis in a non-random manner and has an unpredictable impact on the power of the statistical analyses. Due consideration of the post-hoc aspects of the process will be given when the results are interpreted. Conclusions will be presented as appropriate to the findings of the sensitivity analysis.

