#### 9.10 POOLABILITY

Poolability of results will be assessed by site. The binary co-primary effectiveness endpoints addressing performance of the toric IOL will be tabulated by site to determine if success rates indicate a difference in effectiveness. Similarly, the degree of superiority of the toric arm in reducing residual cylinder, compared with the control arm, will be tested. Cross-tabulations of site by binary endpoints will be analyzed with a Fisher's exact test and the comparison of residual cylinder between treatment arms will be analyzed with an analysis of variance model with an interaction term for site by treatment. In both cases, a p-value of 0.15 will indicate that potential site differences exist and will require investigation as to the possible causes.

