7 ANALYSIS POPULATIONS AND VISIT WINDOW

7.1 ANALYSIS POPULATIONS

The All-enrolled population includes all subjects who sign an informed consent form. This population will be used for disposition summaries.

The Safety population will include all subjects where the test or control IOL touched the eye.

The intent to treat (ITT) population includes all randomized subjects. Missing data will be imputed. Subjects will be analyzed as randomized. The ITT population is the primary analysis population for assessing effectiveness.

The All-implanted population includes all ITT subjects who were successfully implanted with one of the two study IOLs and who attended at least one postoperative visit. Missing data will be imputed. Subjects will be analyzed as randomized. The All-implanted population is supportive of the ITT population for assessing effectiveness.

The Per-Protocol (PP) population includes all subjects in the All-implanted population who have no major protocol deviations that could affect the interpretation of effectiveness and have attended the Form 4 visit. Exclusions from PP will be determined prior to study unmasking. Missing data will not be imputed. Subjects will be analyzed as treated. Analyses based on PP will be supportive of those based on All-implanted.

The Best Case Set will include subjects in PP with all of the following characteristics:

- No major protocol deviations potentially affecting any of the primary effectiveness endpoints (BCDVA, DCNVA). Major protocol deviations that may potentially affect the primary effectiveness endpoints include, but are not limited to:
 - Inclusion of ineligible subjects
 - Implantation of incorrect IOL
 - Missed assessments for effectiveness endpoints at Form 4
 - Receipt of medication likely to interfere with visual performance at Form 4
- One eye implanted with a study lens
- No clinically significant preoperative ocular pathology in the study eye, including any of the following present prior to the operative visit
 - Pseudoexfoliation
 - Glaucoma
 - Uveitis
 - Retinal detachment
 - Diabetic retinopathy
 - Macular degeneration
 - Amblyopia
 - Other preoperative pathologies that are likely to affect central acuity
- No macular degeneration detected at any time in the study eye
- No previous surgery for the correction of refractive errors in the study eye

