8 DATA ANALYSIS METHODS

8.1 DATA AND ANALYSIS CONVENTIONS

The following are some basic stipulations that, unless otherwise stated, apply by default throughout the plan.

- For the co-primary endpoints, the six-month postoperative visit (Form 4) will be the primary analysis time point unless otherwise noted. For the primary safety endpoints, the Form 4 visit will be the primary analysis time point.
- Monocular safety and effectiveness analyses will compare the test group and the control group.

- For all visual acuity-related endpoints in the study, best corrected distance visual acuity (BCDVA) and uncorrected distance visual acuity (UCDVA) are measured at 4 m using a ETDRS chart under photopic conditions. All postoperatively measured visual acuities are recorded and analyzed in logMAR for all endpoint analyses, summary statistics and calculations, and may be converted to Snellen equivalent values for tables, listings, and graphs.
- Safety data will not be imputed, although incomplete or missing dates may be imputed.
- Partial dates will be imputed for safety and effectiveness data, using the most conservative approach available; for safety data, dates will be imputed to result in the longest possible duration of a given adverse event; for effectiveness data, dates will be imputed to maximize the number of study days from the operative date.
- Partial dates in other contexts (e.g., medical history) will be imputed in a way to allow reasonable interpretation, such as to replace the missing date or the missing month with “1.” For example, a partial date recorded as “(missing date)/(missing month)/2020” will be imputed as “1/1/2020” and will be noted as “imputed” on any line listing.
- The expression “summary statistics” indicates sample size (N), mean, standard deviation (SD), median, minimum (Min), and maximum (Max) as applied to continuous variables, and indicates sample size (N), frequency and percent of relevant total as applied to categorical and some ordinal variables.
- All co-primary effectiveness and safety endpoints have to be met to claim overall effectiveness and safety success. Additional analyses and supportive analyses should not be used for the purpose of claims. Under this plan, type 1 error rates will be controlled at a significance level of 0.05 per individual hypothesis without adjustment for multiplicity.
- Data will be pooled across sites for overall analyses unless contraindicated by the poolability analysis in Section 7.8.1.

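### SAP 8.7.1 requires a divergent site to be dropped from the study-level results if a non-device cause is judged most plausible, which conflicts with the all-randomized ITT primary analysis

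*SAP*

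**What the plan says.** **The rule.** SAP 8.7.1 compares treatment effects across centers. It names UCDVA, BCDVA and residual cylinder as examples, with ANOVA at 0.15 for acuity and a "Wilcoxon rank-sum test at $\alpha = 0.15$ for residual cylinder". If the test is significant, the divergent center is identified and causes external to the device are sought, such as staff inconsistency, measurement technique or equipment malfunction. "If such a cause has been identified as the most plausible cause for the divergent treatment effects", then "the analysis center(s) with extreme results will be reported separately and will be excluded from the study-level results".

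**Its reach.** SAP 8.1 states: "Data will be pooled across sites for overall analyses unless contraindicated by the poolability analysis". The cross-reference there is to Section 7.8.1, but the poolability text is Section 8.7.1.

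**The population.** SAP 7.1 states: "The intent to treat (ITT) population includes all randomized subjects". SAP 7.1 and 8.4 make ITT the primary population for effectiveness, with no exception for excluded sites.

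**The protocol.** Protocol 9.10 uses Fisher's exact test for the binary endpoints and an analysis of variance with a site-by-treatment interaction for residual cylinder. Its consequence is limited: "In both cases, a p-value of 0.15 will indicate that potential site differences exist and will require investigation as to the possible causes". The SAP introduction says that the SAP's methods supersede the protocol's.

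**The SAP's own caveat.** SAP 8.7.1 notes that the process "may exclude subjects from the analysis in a non-random manner and has an unpredictable impact on the power of the statistical analyses". It adds: "Due consideration of the post-hoc aspects of the process will be given when the results are interpreted".

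**The concern.** Whether a site's randomized subjects count would depend on a judgement about cause that is opened by that site's own result. No one is named to make the judgement, no standard of evidence is given, and nothing requires it to be made masked. By contrast, SAP 7.1 fixes per-protocol exclusions before unmasking.

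A treatment effect by site cannot be computed without the treatment codes, and Protocol 9.1 places all analysis after database lock. In practice the decision would therefore be made with the results visible. That is an inference from these passages; the SAP does not say it.

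At stake is which result decides the trial. SAP 7.1 and 8.4 say all randomized subjects. SAP 8.7.1 with 8.1 says all except those at excluded sites. If a site is excluded, both cannot be followed, and the document that adds the exclusion is the one that governs. One investigator may implant up to 25% of subjects (SAP 6.2), so one exclusion could remove 0.25 × 230 = 57.5, that is up to 57 randomized subjects.

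**Working it through.** **1. The plan's own figures.** Overall power: 0.94 × 0.99 × 0.99 × 0.99 = 0.912, stated as 91%. Completers: 230 × 0.87 = 200.1, stated as 200. Exact power for co-primary 4 (true rate 91.46%, target 90%) is 98.9–99.6% over n = 100 or 115 and a one- or two-sided 95% bound; 99% is stated. All three reproduce. The 0.94 for co-primary 1 cannot be checked because its inputs are redacted. The stated power calculation makes no allowance for site exclusion.

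**2. How often the screen triggers with no true site differences.**
- One test: 15%.
- Three independent tests: 1 − 0.85³ = 0.386.
- Three tests with an assumed correlation of 0.6: about 29–32%.

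These are rates of opening an investigation, not of excluding a site.

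**3. Exact counts for a binary endpoint.** Protocol 9.5 and 9.8 pass an axis endpoint if the upper 95% Clopper-Pearson bound of the success rate reaches the target. Assumptions: 100 toric eyes (half of 200) and a one-sided 95% bound. For x successes in n, the bound is the 0.95 quantile of Beta(x + 1, n − x).

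| Eyes | Failures | Success rate | Upper bound | 90% target |
|---|---|---|---|---|
| 100 | 15 | 85.0% | 90.5% | pass |
| 100 | 16 | 84.0% | 89.7% | fail |
| 90 (10-eye site dropped, 2 failures) | 14 | 84.4% | 90.3% | pass |
| 75 (25-eye site dropped, 4 failures) | 12 | 84.0% | 90.5% | pass |

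With all 115 toric eyes the pattern is the same: 18 failures fail, and dropping a 12-eye site with 2 of them leaves 16 of 103, which passes. For the 95% target, 10 of 100 fails (bound 94.5%), and dropping a 10-eye site with 2 failures leaves 8 of 90, which passes (bound 95.5%). With a two-sided 95% bound the pass marks move by one failure, but the dropped site needs the same number of failures.

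**4. Type I error for co-primary 1.** Simulated under no treatment effect and no true site differences: 200 eyes, equal sites, normal data with SD 1 (the planning values are redacted), Wilcoxon test at one-sided 0.025, site-by-treatment F test at 0.15, and one site always dropped when flagged. With 8,000 runs the Monte Carlo standard error is √(0.026 × 0.974 / 8,000) ≈ 0.002.

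| Layout | All sites kept | Most extreme site dropped, either direction | Least favorable site dropped |
|---|---|---|---|
| 10 sites, 10 per arm | 0.026 | 0.030 | 0.036 |
| 5 sites, 20 per arm | 0.027 | 0.036 | 0.042 |

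The rule works in both directions. With standardized effects of 0.2–0.3 and no true site differences, dropping the most extreme site turns a fail into a pass in 1.9–3.0% of trials and a pass into a fail in 1.4–3.1%.

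**5. Shift in the estimate.** Assuming 10 sites, 10 eyes per arm per site and SD 0.4 D, the standard error is 0.4 × √(2/100) = 0.057 D. Among flagged trials, always dropping the least favorable site moves the estimate by +0.042 D. Dropping the most extreme site in either direction moves it by about 0.001 D on average.

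**6. The residual-cylinder screen.** A rank-sum test compares two groups. The question is whether the difference between arms varies across up to 10 sites, which is an interaction. The rank-sum test cannot answer it; the model in Protocol 9.10 can.

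**The case against.** The strongest defense is that exclusion is gated. It needs a significant screen, an identified center, a further clinical investigation, and a cause unrelated to the device judged most plausible. A reader might infer that sites can be removed simply for extreme results; the text does not support that. The gate stands, but it is a judgement without criteria, made once the site already looks extreme.

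Other stronger readings also go too far:

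- **That the SAP schedules the decision after unmasking.** No passage says so. It follows from the need for treatment codes and from analysis after lock.
- **That the ITT definition is broken.** SAP 7.1 and 8.4 keep it intact, and Appendix B plans ITT effectiveness tables. The defect is an unresolved conflict between sections. Parts of SAP 8.4 and Appendix B are redacted, so whether all-site results would also be tabulated cannot be checked.
- **That the rule favors the test lens.** It is not directional. The +0.042 D shift arises only if the least favorable site is always the one dropped, and only in the roughly 15% of trials flagged.
- **That about 39% of trials would lose a site.** That is the trigger rate for an investigation, under independence.
- **That the SAP concedes non-random exclusion will occur.** It says only that the process may have that effect.

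The axis counts in the check also need the site to be flagged first. The SAP names between-arm acuity and cylinder effects as examples; Fisher's test on the binary endpoints is in the protocol only.

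SAP 8.7.1 closes by mentioning a sensitivity analysis, which allows a softer reading. But it defines no such analysis and does not say that the all-site result decides, while its operative sentence points the other way.

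**Conclusion.** The concern holds in this limited form. As written, the SAP requires a divergent site to be excluded from the study-level results on an unstructured judgement of cause, and it does not reconcile this with an ITT primary analysis of all randomized subjects. It goes further than the protocol, and its caveats acknowledge the problem without controlling it.

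The inflation of type I error is real but modest: from about 0.026 to 0.030–0.036 under non-directional dropping, with 0.042 as the extreme case. Both assume that a cause is found every time, equal sites and normal data. The exact counts show that a binary endpoint close to its limit can change from fail to pass with only 2 failures in a dropped 10-eye site. They show that this is possible, not how likely it is.

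The rank-sum criticism is a separate method error and stands on its own. Both points should be settled before unmasking, because a later choice between the two results would not be credible.

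**What to change.** - **SAP 8.7.1:** delete the sentence that excludes centers from the study-level results.
- **SAP 8.1:** delete the clause that makes pooling conditional on the poolability analysis. Its wrong section reference goes with it.
- **Add for effectiveness:** the primary ITT analyses include all randomized subjects from all sites and decide success, whatever the poolability result.
- **Add for safety:** no site is removed from the co-primary safety analyses on poolability grounds. Each keeps its own defined population (Safety, All-implanted or Best Case), so the all-randomized statement should not be extended to them.
- **Add for site exclusion:** any analysis without a divergent site is a labelled sensitivity analysis, shown beside the all-site result.
- **Residual cylinder:** restore the site-by-treatment interaction model of Protocol 9.10, on ranks if preferred, in place of the rank-sum test.

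The cost is a SAP wording change and one extra sensitivity table if a site is flagged. Sample size, visits and data collection do not change.

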8.7.2 Stratification Analysis

Specific endpoint values at Form 4 will be stratified by preoperative keratometric cylinder. These include reduction of 0.5D cylindrical power as a binary endpoint, absolute reduction in cylindrical power, logMAR UDVA, and manifest refractive cylinder. Additional stratifications will be by age (per section 8.1 categorization), race, and ethnicity.

8.7.3 Interim Analysis

No interim analysis is planned.

9 SOFTWARE

The analyses described in this SAP will be performed using SAS/BASE and SAS/STAT software, Version 9.4 of the SAS System for Windows (Operating System: Windows 11 Professional 64-bit). Copyright© 2018 SAS Institute Inc. SAS and all other SAS Institute Inc. Cary, NC, USA. Other software may be used including R Version 4.3.0 (The R Foundation for Statistical Computing, 2023, platform: x86_64-apple-darwin20 (64-bit)).

APPENDIX A – SCHEDULE OF ACTIVITIES

Examination		Pre-operative/Screening Visit	Form 0	Form 1	Form 2	Form 3	Form 4	USV ¹
Informed Consent and HIPAA		X						
Demographics		X						
Inclusion & Exclusion Criteria Evaluation		X						
Inclusion & Exclusion Criteria Review			X					
Ocular and non-ocular Medical History		X						
Urine Pregnancy Test (if applicable)		X						
Potential Visual Acuity		X						
Target Refraction		X						
IOL power calculation		X						
Axial Length and Anterior Chamber Depth		X						
Keratometry measurement		X				X	X	X
PhysIOL Toric Calculator		X						
Corneal Topography		X						
Manifest Refraction (ETDRS)-4 meters		X			X	X	X	X
Randomization		X						
Operative Procedures			X					
Intraocular Pressure		X		X	X	X	X	X
Slit Lamp Examination		X		X	X	X	X	X
IOL Tilt and Decentration Grading				X	X	X	X	X
IOL Axis Orientation ²			X	X	X	X	X	X
Dilated pupil size		X						
Dilated Fundus Examination		X				X	X	X
IOL Observations				X	X	X	X	X
Adverse Events		X	X	X	X	X	X	X
Device Deficiencies			X	X	X	X	X	X
Concomitant Medications		X	X	X	X	X	X	X
Exit from Study							X	
Visual Acuity	UCDVA	X		X	X	X	X	X
	BCDVA	X			X	X	X	X

¹USV- Unscheduled Visit; specific assessments to be completed may be determined by the investigator as appropriate based on the subject's condition. Recommended assessments for Investigator consideration are denoted in the table.

²Subjects must be dilated for IOL axis of orientation assessment.

APPENDIX B – PLANNED TABLES AND FIGURES

Below is a listing of the main tables and figures planned to summarize and illustrate the key outcomes and statistical analysis of the present study. Administrative tables (14.1.x) will be summarized for the Safety, ITT, All-implanted (if different from ITT), and PP analysis populations. Effectiveness tables (14.2.x) will be summarized by ITT, All-implanted, PP, and best case populations. Safety tables (14.3.x) will be summarized using the Safety population. Line listings will be provided in support of all summary tables.

114

[REDACTED]

██████████

15 JULY 2004
